Helen Joseph Hospital is approximately 4 km west of Johannesburg's inner-city in the suburb of Auckland Park. As a tertiary clinical site, the hospital provides a number of clinical services including HIV, ANC, PNC, and specialised care services to patients and has a connection with the University of Witwatersrand's Department of Medicine. The area surrounding Helen Joseph Hospital is comprised of mostly black South African middle-income families living in single unit residential dwellings. Helen Joseph Hospital has a catchment population of around 250,000 and an HIV prevalence of approximately 15-20%.

Linkage-to-care rates for all newly diagnosed HIV-positive individuals in both sites are 50-55%. Women have slightly higher linkage rates, at 60%, while men have slightly lower rates, close to 45%. Exact linkage-to-care figures for young adults, those aged between 18 and 25, in this area are unknown. However, previous research has suggested linkage rates for young adults to be 40-45% (Takuva et al 2015). Due to South African laws that protect exploitation of children and the resulting difficulty in including them in research studies, all participants will be 18 years of age or older.

Intervention

This is a multi-site randomised controlled trial in which newly diagnosed HIV-positive patients, fulfilling all inclusion criteria, will be randomised to either receive the intervention (installation of a password-protected laboratory result and HIV-information app on their smartphone) or the standard of care. All patients will be provided with their unique identifier, to present to the clinic, and asked for permission to access their results on the computer, as a means to assess follow up, to phone them and ask them about their experience of HIV care (at the end of the study) and to verify their clinic attendance throughout the study. Participants will be able to provide feedback about the study to the study team by phone or SMS at any time. In return for their time all study participants will receive a R50 study participation allowance, in the form of a mobile phone credit voucher, at the end of their recruitment visit. Participants will be informed that no additional funds will be provided for subsequent appointments.

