With additional funding the study will include a patient follow-up 12 months after recruitment. Patients will be contacted by phone and asked to complete the WHO Quality Of Life BREF HIV tool (WHOQOL-BREF HIV⁴), those on ARVs will be given the ACTG ARV adherence tool while all participants will be asked to provide their feedback through an end-of-study questionnaire. The end of study questionnaire includes questions regarding their experiences during the study, their health status, their experience of HIV care, actual and opportunity costs, as well as a follow-up HIV/CD4 count knowledge questionnaire (tools can be found in appendix II). All responses will be recorded into REDCap on a mobile device by research staff.

Cost-Effectiveness analysis

A cost-effectiveness analysis will be conducted and compare the intervention arm with the standard of care arm from the societal perspective. Financial and economic costs will be assessed, which include ART costs, incremental health systems costs, and patient productivity loss due to morbidity and mortality. A potential for cost savings due to a reduction in low CD4 count results, Adverse Event (AE) and Opportunistic Infection (OI) will also be incorporated into the cost-effectiveness analysis.

Populations under consideration:

- General population
- General population categorised by 5 year age groups
- Specific populations: 18 to 25, over 25, men

Epidemiology outcomes:

- HIV mortality by 5 year age groups
- HIV incidence by 5 year age groups

⁴ The WHOQOL-BREF HIV is a cross-cultural quality of life assessment tool based on the WHO-QOL100 and the WHO-QOL-BREF. The WHO-QOL-BREF HIV measures quality of life for those with HIV over 31 questions.

- HIV prevalence by 5 year age groups
- Rate of progression to death through four equal durations
- HIV stages defined by mean CD4 count

Economic outcomes (to be obtained through the patient chart review include):

- ARV drug costs
- Treatment literacy level
- Clinic consultations (for ART delivery and OI and AE treatment)
- Laboratory tests (including CD4, viral load and routine monitoring tests)
- X-rays
- Diagnostic procedures
- Personnel training costs
- Number of consultations with i) doctors; ii) nurses consultations; iii) other health care personnel
- Number of home visits
- Number of counsellor consultations

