- Total annual per patient cost of providing a comprehensive model of ART linkage to care using the smartphone app (receiving laboratory results and linkage-to-care) plus cost over 10 years

Cost-effectiveness analysis involves the comparison of two or more competing methods in terms of both their costs and consequences. The outcome measure of the cost-effectiveness work will be the cost of ART initiation with a particular intervention in South African Rand (ZAR) per disability adjusted life year (DALY) averted. The lower the cost per DALY averted, the more cost-effective the intervention. It will be based on a 5% discount rate.

For each target and cost scenario, this analysis will be able to provide the estimated impact in terms of OI and AE averted, impact in HIV stage defined by CD4 count and treatment costs and deaths averted due to ART linkage to care of those using the smartphone app.

Participant opt-out

All participants will be provided with contact information for the study team and will be informed that they can drop out of the study at any time with no consequences (as per Good Clinical Practice guidelines). Should a participant request to withdraw from the study the team will identify their informed consent sheet and mark it accordingly, remove the patient's data from REDCap and notify the NHLS if they are part of the intervention arm to ensure they will not receive additional notifications of laboratory results. The participant will be asked if they would like to keep their username and password active to access the app in the future; their account will be deleted or kept accordingly.

Safety considerations

Accidental disclosure (through phone loss/theft/borrowing or any other method) will be limited by the study team as much as possible. This will be done actively by having a username, password AND PIN code for app use. Additionally, the recruitment team will inform participants of the sensitive information on the app and request that they don't share it with

anyone. Lastly, the app icon and name will not relate to health or HIV in any way; only after the username and password is entered will health-related terminology be used.

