From the opportunity cost data collected from patients we will analyse clients' time spent travelling to and being at health facilities to assess service uptake to measure actual patient opportunity cost. The team will separate costs of implementing the SmartLtC intervention and standard of care into categories (e.g. ART, other medicine, laboratory & other tests, health personnel time, overhead and capital costs, patient transport, and lost patient time) which will come from the WHO CHOICE database. Additionally, we will calculate DALY's saved based on disability and deaths averted due to the intervention with weights based on the 2010 Global Burden of Disease Study.

Regulatory compliance

The following methods will be employed to ensure high quality assurance throughout the study period:

- All study staff are GCP trained and certified throughout the study period.
- The study will not start before it receives ethics permission from the University of Witwatersrand Human Research Ethics Committee (Medical) and approval from the district research committee.
- All data collected for the study will be treated sensitively and stored in a secure location (for paper documents) or a secured, password and encrypted database (for electronic records)

Ethics

As a research institute, all RHI research projects go through both internal and external research review. The external review is done through the University of Witwatersrand's ethics board, the Human Subjects Research Committee (HSRC). The SmartLtC study will not start recruiting patients before the committee has reviewed the study and has provided ethics clearance.

Informed consent forms

Informed consent form can be found at the end of this document in Appendix I.

Expected outcomes

This study is expected to have the following outcomes by the end of the project:

- An analysis of the effect of the app in linkage to care for the study population and in different demographic and socioeconomic subgroups
- An understanding of the acceptability of the laboratory result app
- Incremental cost-effectiveness ratio for SmartLTC compared to SOC from the societal perspective and the DOH perspective
- One or more conference presentations on the study and outcomes
- One or more published academic journal articles describing the study and outcomes
- A study report providing recommendations to policy makers, other study teams, and health practitioners.

Dissemination of results and publication policy

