3.3 Statement of null and alternate hypotheses

The analysis of will include the following test of hypothesis:

H_0 : $\mu_{\text{Attendance to a second NHLS blood test within 8 months (Control)}} = \mu_{\text{Attendance to a second NHLS blood test within 8 months (Intervention)}}$

H_A : $\mu_{\text{Attendance to a second NHLS blood test within 8 months (Control)}} \neq \mu_{\text{Attendance to a second NHLS blood test within 8 months (Intervention)}}$

STATISTICAL ANALYSIS PLAN

SmartLtC: Does an Android Smartphone App Increase Linkage To Care in Johannesburg

Acceptance of the H_A will be considered to be a successful demonstration of difference between the intervention and control arms

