4.3 Randomisation and blinding

4.3.1. Patients were randomised through the REDCap system with no blinding

5. SAMPLE SIZE

Recruitment for this trial showed that achieving a sample size for any sub-group analysis is difficult to achieve with an app limited to a subset of smartphones in circulation and several other eligibility criteria on age, residence, literacy, and having a smartphone with data. Section 7.1. shows the flowchart of the HIV cases as they are screened and assessed for eligibility, then randomised and followed up. Priority groups of interest to this trial are males and young HIV clients aged 18-30 years, and it is exactly these two groups which are also more difficult to screen for eligibility as they use HCT services to a lesser extent.

The recruitment over approximately 8 months is expected to be able to recruit about 350 individuals. While it would be desirable to recruit a larger sample, as decision was made to stop at a time when sufficient sample is achieved to detect any effectiveness of the app (based on a 20% difference in linkage to care between the intervention and control arm, an 80% power with significance level of 0.05). At this sample size, it will be possible to see any trends in linkage to care in the priority sub-groups (males, youth) between the two trial arms, but the sub-groups will not be large enough to detect a 20% difference with statistical accuracy.

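### Cost per DALY averted is the stated cost-effectiveness result, but about 350 participants cannot show deaths averted, no model is named to supply them, and chart-recorded illness depends on being in care

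*Protocol*

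**What the plan says.** Secondary objective 9 of the protocol, kept as SAP 3.2.9, is the incremental cost and cost-effectiveness of app-linked ART initiation against standard initiation. The protocol's Cost-Effectiveness analysis section gives the outcome as the "cost of ART initiation with a particular intervention in South African Rand (ZAR) per disability adjusted life year (DALY) averted". The Analysis plan adds: "we will calculate DALY's saved based on disability and deaths averted due to the intervention".

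The Cost-Effectiveness section also:

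- lists epidemiology outcomes, including mortality, prevalence and "HIV incidence by 5 year age groups";
- counts possible savings from fewer low CD4 results, AEs and OIs;
- assigns economic outcomes to chart review, where OIs and AEs appear as clinic consultations for their treatment.

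The only outside sources named are WHO CHOICE for costs and the 2010 Global Burden of Disease Study for disability weights.

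SAP section 5 says recruitment "is expected to be able to recruit about 350 individuals", against at least 1000 per arm in the protocol. Follow-up is stated in three ways: at least 8 months, with 12 more if funded (Duration); a 12-month telephone contact if funded, and one year to 18 months (both under Patient follow-up). The SAP's outcome variables, tests and dummy tables (3.4, 3.5, 6.6, 7) contain no economic analysis.

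**The concern.** A ratio per DALY averted needs an estimate of deaths and disability averted. Either the trial supplies it or a model does. The trial is small and short, and neither document describes how deaths would be found. The survey tools in Appendix II have no vital-status or OI item, and missing data are classed as loss to follow-up. If a model is to supply it, no structure, effect horizon, mortality or OI input, or path from linkage to DALYs is given.

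The AE, OI and low-CD4 savings raise a separate problem. These events are recorded when someone attends care, and attending care is what the app is meant to change. For low CD4 the overlap is close to complete: the Sample Size section has pre-ART patients returning for a follow-up CD4, and that return test is itself the primary endpoint event.

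The protocol says the team will seek national rollout if linkage improves. A cost per DALY presented as trial evidence could carry weight in that decision which the data cannot bear.

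**Working it through.** **The plan's own figure.** No sample size or precision is given for deaths, DALYs, OIs or cost-effectiveness. The 350 is justified for linkage only, "based on a 20% difference in linkage to care between the intervention and control arm, an 80% power with significance level of 0.05". The protocol says "Linkage-to-care rates for all newly diagnosed HIV-positive individuals in both sites are 50-55" per cent. Taking the difference as 20 absolute points, a two-sided pooled two-proportion calculation needs 93 per arm from 50% and 89 from 55%. With 175 per arm (1:1 allocation assumed; the ratio is not stated) power is 97-98%. So 350 is adequate for linkage if the 20% is absolute. If it is relative, power is 47-56%.

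**Deaths averted.** The documents give no mortality rate, so a range is assumed. Let u be the death risk over follow-up in unlinked people and r × u the risk in linked people. Linkage is 52.5% (midpoint of 50-55%) in controls and 72.5% with the app.

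- Control risk = u × (0.475 + 0.525r)
- App risk = u × (0.275 + 0.725r)
- Deaths averted per 175 = 175 × 0.20 × u × (1 − r)

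| u | r | Control risk | App risk | Averted per 175 | 95% half-width | Power | Per arm for 80% |
|---|---|---|---|---|---|---|---|
| 1% | 0.5 | 0.74% | 0.64% | 0.2 | 3.0 | 3% | 107,179 |
| 5% | 0.5 | 3.69% | 3.19% | 0.9 | 6.7 | 4% | 20,842 |
| 15% | 0.5 | 11.06% | 9.56% | 2.6 | 11.1 | 7% | 6,452 |
| 1% | 0.25 | 0.61% | 0.46% | 0.3 | 2.7 | 4% | 36,867 |
| 15% | 0.25 | 9.09% | 6.84% | 3.9 | 9.9 | 12% | 2,273 |

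In every row the half-width exceeds the effect. Because u is the risk over whatever follow-up is achieved, the table serves for 8, 12 or 18 months.

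**Chart-recorded OIs.** Assume an OI risk of 10% in linked and 20% in unlinked people, and let c be the share of unlinked people's OIs that reach a chart.

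- Control, recorded = 175 × (0.525 × 0.10 + 0.475 × 0.20 × c)
- App, recorded = 175 × (0.725 × 0.10 + 0.275 × 0.20 × c)

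| c | Control | App |
|---|---|---|
| 0 | 9.2 | 12.7 |
| 0.5 | 17.5 | 17.5 |
| 1 (true counts) | 25.8 | 22.3 |

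The app truly prevents 3.5 OIs per 175, but with no capture the charts show 3.5 more. The counts are equal when c equals linked risk divided by unlinked risk, here 0.10/0.20 = 50%. Above that the charts favour the app.

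**Participants linked.** The difference is 0.20, with SE = √[(0.525 × 0.475 + 0.725 × 0.275)/175] = 0.0506, so the 95% interval is 0.20 ± 0.099. Per 175 that is 35 more linked, 95% CI about 18 to 52.

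**The case against.** The strongest reply is that the epidemiology list was never meant to be observed in the trial. It follows directly on populations given as the general population and its five-year age groups, and the section goes on to a 5% discount rate, costs over 10 years and estimated impact for each target and cost scenario. That is the language of projection, and it largely stands. A reader might infer that the plan tries to measure HIV incidence and prevalence in people who are all HIV-positive at entry. The documents do not clearly say so; these are more probably model outputs that are not labelled as such.

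For the same reason, a reader might infer that the ratio's denominator would have an almost random sign. That follows only if DALYs are computed from raw trial death counts, which no passage states.

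A third tempting reading is that chart data must count against the app arm. That is too strong. Linkage is defined by laboratory tests, so an unlinked person may still attend and have an OI charted, and the direction turns on how often this happens. Extra visits, tests and ARV costs in the better-linked arm are real incremental costs and not bias.

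Silence about vital status is also not proof that deaths go unseen: chart review and, if funded, a 12-month call might find some. And this is a secondary objective that leaves the primary result untouched.

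None of this closes the gap. Intending a model is not specifying one, and no ascertainment independent of linkage is described.

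**Conclusion.** The concern holds in this form: the stated effect measure cannot be obtained from the trial, and the means of obtaining it elsewhere is not specified. Power of about 3-12% for deaths rests on assumed death risks of 1-15% in unlinked people, half or a quarter of that in linked people, 175 per arm, and an effect acting only through 20 points more linkage. A direct halving of mortality would be easier to detect, but even then power is 6% to 57% for assumed control mortality of 1-10% a year over 8 to 18 months.

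Differential ascertainment of OIs and AEs is a structural risk. That it would disfavour the better-linked arm is likely but not certain; in the example it reverses above 50% capture, a threshold set by assumed OI risks.

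Additional participants linked is well estimated at this sample size if the effect is near the planned one. The issue is worth correcting because the remedy is cheap, not because it threatens the main conclusion.

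**What to change.** Amend the protocol's Cost-Effectiveness analysis and Analysis plan, and add an economic section to the SAP:

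- Make the within-trial result the incremental cost per additional participant linked at 8 months, in all randomised participants, with a bootstrap interval. Put cost per additional ART initiation second. Report the cost difference and the linkage difference separately as well, since a ratio becomes unstable if the linkage effect is small.
- Do not estimate OI, AE or low-CD4 effects by arm from the charts of people in care. If OIs or deaths are to be compared at all, define ascertainment that is identical in both arms whatever the linkage status.
- Label mortality, incidence, prevalence, OIs averted and cost per DALY as outputs of a pre-specified model. It should be driven by the trial's linkage effect, with stated structure and horizon, named outside inputs and uncertainty analysis.
- State how costs are obtained for participants without a chart. Patient time and travel costs come from an end-of-study interview that depends on further funding, so say what is reported if it does not take place.

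The cost is protocol and SAP wording, work to specify the model if cost per DALY is kept, and somewhat less chart abstraction. The loss is that cost per DALY can no longer be presented as a result of trial data.

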Appendix II: Participant survey tools

	Population survey (To be given to all newly diagnosed HIV-positive patients that have had CD4 count bloods drawn)
1	Recruitment Date:
2	Recruitment site:
3	Gender:
4	Date of birth:
5	Marital status:
6	Suburb currently living in:
7	Country of birth:
8	Highest education received:
9	What is your current employment status?
10	Usual monthly household income: (Note: still being reviewed based on discussions around Proxy Means Test method)
11	Preferred language for reading:
12	Do you share your phone with someone?: Y/N
13	Do you own a smartphone? Y/N
14	Do you use data on your smartphone (eg: WhatsApp, WeChat, Mxit, web page, email)?

	Recruitment survey (To be given to all eligible and willing participants)
1	First name:
2	Last name:
3	Phone number:
4	SA ID, Passport or refugee number:
5	Lab Specimen ID number:

6	WHO staging on patient chart: 1, 2, 3 or 4
---	--

	Reason for ineligibility survey (To be given to ineligible patients)
1	Age - Under 18
2	Phone - Not Android/Not working/Not active
2a	Type of phone:
3	No photo proof of identity
4	Cannot read English or Zulu
5	Not willing/unable to sign informed consent
6	Pregnant
7	Refused to participate

	HIV/CD4 Count/VL knowledge All answers are true/false (Correct answer in parentheses) (To be given at baseline and end of study for all participants)
1	A healthy-looking person can have HIV. (True)
2	Coughing and sneezing DO NOT spread HIV. (True)
3	A person can get HIV by sharing a glass of water with someone who has HIV. (False)
4	A woman can get HIV if she has anal sex with an HIV positive man. (True)
5	Showering, or washing one's genitals/private parts, after sex keeps a person from getting HIV. (False)
6	A pregnant woman infected with HIV and taking medicines will always have a baby born with HIV. (False)
7	People who have been infected with HIV quickly show serious signs of being infected. (False)
8	A woman cannot get HIV if she has sex during her period. (False)
9	There is a female condom that can help decrease a woman's chance of getting HIV. (True)

10	A person will NOT get HIV if she or he is taking antibiotics. (False)
11	A person can get HIV from oral sex. (True)
12	HIV can be transmitted through vaginal sex without condoms. (True)
13	HIV cannot be transmitted through use of public toilets. (True)
14	HIV cannot be transmitted through sweat. (True)
15	Use of birth control pills cannot prevent people from getting the HIV/AIDS virus. (True)
16	There is no vaccine available that can keep people from getting AIDS. (True)
17	Antiretroviral drugs keep people living with HIV/AIDS. from getting sick or dying. (True)
18	HIV can be transmitted by eating and drinking from the same plate or glass of an HIV-positive person. (False)
19	HIV can be transmitted through a mosquito bite. (False)
20	HIV can be prevented by properly using condoms during sexual intercourse. (True)
21	Antiretroviral drugs can cure HIV/AIDS. (False)
22	Antiretroviral drugs can prolong the life of people infected with HIV/AIDS. (True)
23	Men and women normally have the same CD4 count. (False)
24	Physical activity can impact CD4 count. (True)
25	A lower CD4 count is better. (False)
26	HIV decreases CD4 count in people who don't take ARVs. (True)
27	A person's CD4 count helps determine if they should be on ARVs. (True)
28	An HIV-negative person always has the same CD4 count. (False)
29	People with HIV who are not on ARVs should check their CD4 count every 6 months. (True)
30	People with HIV are more likely to get other diseases like TB. (True)
31	A viral load test determines how much HIV is in the blood. (True)
32	CD4 counts and viral load tests don't help HIV infected people at all. (False)
33	A higher viral load is better. (False)
34	Someone who takes their ARV medicine regularly will likely end up with an 'undetectable' viral load. (True)

	WHOQOL-BREF HIV (To be given at end of study for all participants)
1	What is your marital status?
2	How is your health (Very poor/Poor/Neither Poor nor Good/Good/Very Good)
3	Do you consider yourself currently ill? Yes/No
4	If there is something wrong with you, what do you think it is?
5	In what year did you first test positive for HIV?
6	In what year do you think you were infected?
	All questions below are Likert-scale (1-5) based on the original WHOQOL-BREF HIV tool
7	How would you rate your quality of life?
8	How satisfied are you with your health?
9	To what extent do you feel that physical pain prevents you from doing what you need to do?
10	How much are you bothered by any physical problems related to your HIV infection?
11	How much do you need any medical treatment to function in your daily life?
12	How much do you enjoy life?
13	To what extent do you feel your life to be meaningful?
14	To what extent are you bothered by people blaming you for your HIV status?
15	How much do you fear the future?
16	How much do you worry about death?
17	How well are you able to concentrate?
18	How safe do you feel in your daily life?
19	How healthy is your physical environment?
20	Do you have enough energy for everyday life?
21	Are you able to accept your bodily appearance?
22	Do you have enough money to meet your needs?
23	To what extent do you feel accepted by the people you know?

24	How available to you is the information that you need in your day-to-day life?
25	To what extent do you have the opportunity for leisure activities?
26	How well are you able to get around?
27	How satisfied are you with your sleep?
28	How satisfied are you with your ability to perform your daily living activities?
29	How satisfied are you with yourself?
30	How satisfied are you with your personal relationships?
31	How satisfied are you with your sex life?
32	How satisfied are you with the support you get from your friends?
33	How satisfied are you with the conditions of your living place?
34	How satisfied are you with your access to health services?
35	How satisfied are you with your transport?
36	How often do you have negative feelings such as sadness, despair, anxiety, depression?

	
Satisfaction survey Likert Scale (1 Strongly disagree - 5 Strongly agree) (To be given at end of study. Note: Questions in bold will only be asked to intervention patients)

1	Overall I am very happy with the study
2	Overall I am very happy with the app
3	The app helped me learn about my condition
4	The app was easy to use
5	The language in the app was easy to understand
6	I felt like I could trust the information in the app
7	I learnt a great deal about HIV in the past 12 months
8	I learnt a great deal about CD4 count in the past 12 months
9	I learnt a great deal about viral load in the past 12 months
10	I would recommend the app to other patients

11	The app made life easier for me
12	The clinic staff was always friendly when received HIV care
13	I feel I know a great deal about HIV
14	I feel I have the tools to keep myself healthy
15	I feel I could help a friend who was HIV-positive
16	I visited the frequently asked questions (FAQ"s) in the app
17	The frequently asked questions (FAQ"s) were helpful
18	The frequently asked questions (FAQ"s) were relevant
19	I read the "More Information" section of the app
20	The "More Information" section of the app was helpful
21	The "More Information" section of the app was relevant
22	The explanation of CD4 count was useful
23	I went to the links to additional sites to get more information
24	The reminder to go for an additional test at 6 months was helpful
25	The reminder to go for the additional tests was useful
26	I would recommend the app to other people
27	The app would have been more useful if it covered other health issues.

	Costs incurred tool (To be given at end of study for all participants)
1	How much do you usually pay per month to support the routine use of your mobile phone (including air time, maintenance, and other costs)?
2	How much money do you usually spend on transportation to attend the HIV clinic?
3	Do you usually take time off from work to attend the HIV clinic?
3a	If yes, how much money or income did you lose because of this absence from work?
4	What is the amount of time (in minutes) you usually spend on your HIV clinic visits from the time you depart (your home, work or elsewhere) to go to the health facility until the time you returned?
4a	Travel time (round trip): _____ Waiting time: _____

	Consultation time: _____ Pharmacy time (obtaining medicines): _____ Total time: _____
5	Did you have to pay someone to take care of any other children while you attended the HIV clinic?
5a	If yes, how much did you spend?
6	How many times have you been to the clinic to receive HIV care since your HIV diagnosis?
7	Did you ever attend the clinic for care and were not seen?
7a	Why were you not seen? - Attended wrong time/day - Clinic too busy - Other: _____

	ACTG Adherence Tool - Standardised HIV treatment adherence tool (To be given at end of study to study participants on ARV medicine)
1	What HIV medicines are you currently taking?
2	How many pills of each do you take each time?
3	How many times a day do you take each of your pills?
4	How many doses of each of your pills did you miss yesterday?
5	How many doses of each of your pills did you miss the day before yesterday?
6	How many doses of each of your pills did you miss three days ago?
7	How many doses of each of your pills did you miss four days ago?
8	During the past 4 days, on how many days have you missed taking all your doses?
9	Most anti-HIV medications need to be taken on a schedule, such as '2 times a day' or '3 times a day' or 'every 8 hours.' How closely did you follow your specific schedule over the last four days?
10	Do any of your anti-HIV medications have special instructions, such as 'take with food' or 'on an empty stomach' or 'with plenty of fluids?'
10a	If Yes, how often did you follow those special instructions over the last four days?
11	Some people find that they forget to take their pills on the weekend days. Did you miss any of your anti-HIV medications last weekend-- last Saturday or Sunday?
12	When was the last time you missed any of your medications?

13	
People may miss taking their medications for various reasons. Here is a list of possible reasons why you may miss taking your medications. How often have you missed taking your medications because you:
 
Were away from home? Were busy with other things? Simply forgot? Had too many pills to take? Wanted to avoid side effects? Did not want others to notice you taking medication? Had a change in daily routine? Felt like the drug was toxic/harmful? Fell asleep/slept through dose time? Felt sick or ill? Felt depressed/overwhelmed? Had problems taking pills at specified times (with meals, on empty stomach, etc.) Ran out of pills? Felt good?

14	
The following questions ask about symptoms you might have had during the past four weeks. Please select, from 1 (I do not have this symptom) to 5 (I have this symptom and it bothers me greatly) the answer which describes how much you have been bothered by each symptom:
 
Fatigue or loss of energy? Fever, chills or sweats? Feeling dizzy or lightheaded? Pain, numbness or tingling in the hands or feet? Trouble remembering? Nausea or vomiting? Diarrhoea or loose bowel movements? Felt sad, down or depressed? Felt nervous or anxious? Difficulty falling or staying asleep? Skin problems, such as rash, dryness or itching? Cough or trouble catching your breath? Headache? Loss of appetite or a change in the taste of food? Bloating, pain or gas in your stomach? Muscle aches or joint pain? Problems with having sex, such as loss of interest or lack of satisfaction? Changes in the way your body looks, such as fat deposits or weight gain? Problems with weight loss or wasting? Hair loss or changes in the way your hair looks?

